## **3 Potential Risks**

#### 3.1 Risk Management

This study is anticipated to have minimal risk to subject safety.

Questionnaire:

The data collection, including demographic data, will be done by approved study personnel using paper or electronic format. For paper collections, all information will be de-identified and kept under double-secured filing systems. For electronic collections, we will be using HIPAA compliant software (i.e. SurveyMonkey, CRIO). Data will be de-identified and stored electronically in a password protected database. Access to the database will be restricted to key personnel of this study. As with all electronically stored data, a breach of security is a potential risk.

#### HRV / Wearable Recordings:

The HRV recording equipment is similar to recording a standard 3-lead ECG. Skin reactions to adhesives in the electrode are a theoretical risk. All wearable equipment is commercially available and cleared.

#### EEG Recordings:

During recording of the EEG, slight headaches in very sensitive individuals may occur. If wearing the EEG equipment on the head cannot be tolerated, the sampling procedure can be stopped immediately. Furthermore, a skin reaction to the electrode adhesive is theoretically

possible.

Biologicals:

Drawing blood always poses a risk of infection and mild discomfort. These will be mitigated by having the blood draws performed by experienced professionals using standard techniques. Saliva collections utilize non-invasive techniques. Collections of this data pose no additional risk.

## **3.2 Potential Benefits**

There will be no direct benefits to participants in this study from the study procedures. However, the data obtained will contribute to future research into the molecular effects of meditation practices.

## 3.3 Risk/Benefit Assessment

The risks of participation are minimal and are offset by the value of the information obtained.

# **4 Eligibility**

Since we propose to look at different cohorts under this protocol, as outlined under Experiment A, B, C, we will follow the same format for Inclusion/Exclusion Criteria.

#### 4.1 Experiment A (Measuring the effects of meditation on the Healer and Healee)

## 4.1.1 Inclusion Criteria

Potential subjects must meet all inclusion criteria:

- 1. Subjects must be a participant in a [name] healing event to qualify as a Healer.
- 2. Subject must volunteer to receive a healing in a [name] healing event to qualify as a Healee.
- 3. Subject or an assigned representative must be willing and able to read and provide Informed Consent in English language.
- 4. Subjects must be 18 years of age or older.

## 4.1.2 Exclusion Criteria

Potential subjects must not meet any exclusion criteria:

- 1. Unable or unwilling to provide Informed Consent.
- 2. Subjects with any medical condition that by discretion of the Principal Investigator would be disqualified.

## 4.2 Experiment B (Measuring the effects of meditation on the human organism)

#### 4.2.1 Inclusion Criteria

Potential subjects must meet all inclusion criteria:

- 1. Subjects must be 18 years of age or older.
- 2. Subjects must be a participant in a [name] meditation event.
- 3. Subject or an assigned representative must be willing and able to read and provide Informed Consent in English language.

Potential controls must meet all inclusion criteria:

- 1. Controls must be 18 years of age or older.
- 2. Controls must be willing and able to read and provide Informed Consent in English language.

#### 4.2.2 Exclusion Criteria

Potential subjects must not meet any exclusion criteria:

- 1. Neurological diagnosis that could interfere/alter with EEG recordings such as epilepsy.
- 2. Subjects who had a heart transplant.
- 3. Subjects who have cardiac disease that could interfere with ECG recording such as but not limited to cardiac arrhythmia or disorder of cardiac conduction.
- 4. Subjects who have been diagnosed with a malignant disease that could interfere with blood parameters.
- 5. Subjects with any medical condition that by discretion of the Principal Investigator would be disqualified.

Potential controls must not meet any exclusion criteria:

- 1. Neurological Diagnosis that could interfere/alter with EEG recordings such as epilepsy.
- 2. Controls who had a heart transplant.
- 3. Controls who have cardiac disease that could interfere with ECG recording such as but not limited to cardiac arrhythmia or disorder of cardiac conduction.
- 4. Controls who have been diagnosed with a malignant disease that could interfere with blood parameters.
- 5. Controls with any medical condition that by discretion of the Principal Investigator would be disqualified.
- 6. Controls must not be a participant in a [name] meditation event.

**4.3 Experiment C** (Measuring the effects of meditation within the meditation community)

#### 4.3.1 Inclusion Criteria

Potential subjects must meet all inclusion criteria:

- 1. Subjects must be a member of [name] meditation community.
- 2. Subject must be willing and able to read and provide Informed Consent in English language.
- 3. Subjects must be 18 years of age or older.

#### 4.3.2 Exclusion Criteria

Potential subjects must not meet any exclusion criteria:

- 1. Unable or unwilling to provide Informed Consent.
- 2. Subjects with any condition that by discretion of the Principal Investigator would be disqualified.

#### 4.4 Subject Withdrawal / Discontinuation

Subjects have the ability to withdraw from the study at any point. Data collected prior to the withdrawal of consent will be stored and potentially used in data analysis.

Subjects may also be discontinued from participating if the Investigator has reason to believe that they are not adhering to study requirements.

#### 4.5 Subject Compensation

- Research subjects will not be compensated for participation in these studies.
- Research controls may receive a modest form of compensation for participation in these studies.

#### 4.6 Alternatives to Participation

The alternative to participating in this research study is to not participate in the research study. Patients will receive no different treatment at the meditation event if they choose not to participate.

## **5 Subject Recruitment**

Subject outreach will utilize [name] online presence (website, social media, etc.). Subjects will be recruited through prescreening emails to members of [name] meditation community and/or registered event participants. These emails will briefly explain the research study and offer the subject the option to follow a link for pre-screening.

For pre-screening, potential subjects will visit a pre-screening questionnaire via a HIPAA compliant software (ie. SurveyMonkey) and be asked general pre-screening questions based on

the inclusion and exclusion criteria. The questionnaire will also collect basic data such as demographics and past medical history.

## 6 Study Design and Procedures

## 6.1 Study Procedures

6.1.1 Experiment A (Measuring the effects of meditation on the Healer and Healee)

Our exploratory study will focus on interactions among Healers and Healees. We are also interested in collecting data among Healers themselves.

6.1.2 Experiment B (Measuring the effects of meditation on the human organism)

Under this paradigm, we will collect data on the effects of meditation on the human organism. We therefore aim to collect data before, during, and after a meditation event that take place nationally and internationally on a regular basis. The environment of an event poses the rare opportunity of minimized confounding factors (i.e. diet, housing, sleep).

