#### 6.3.2 Experiment B (Measuring the effects of meditation on the human organism)

Subject selection: Pre-event, registered participants [name] event will be contacted (i.e. email) and made aware of the research opportunity. Registered participants who are interested will be able to follow a link to a pre-screening questionnaire. Members of [name] meditation community who pass pre-screening qualify to participate. Depending on the event, we anticipate recruiting between 10 to 100 subjects.

Control Selection: In addition, we will identify controls by asking participants if they are traveling with family/friends who will be at the event but will not participate in the event; these may be volunteers of the event, and/or family/friends of meditators participating in the event. Controls will be age and sex matched to match subjects. We anticipate recruiting between 5 and 20 control subjects. The consenting as well as some baseline data (i.e. Medical history, demographics) collection will be performed electronically prior to the event.

Pre-event: Consenting: The consent form will be provided to the selected subjects for review prior to the event. The PI or designated research staff member will go over the consent form in person or via HIPAA compliant web meeting platform (i.e. Zoom). During this time, subjects will have ample time to have all questions and concerns addressed. We may also collect baseline

measures including physiological readouts (i.e. wearables, HRVs) and/or biological data (i.e. saliva).

Immediate Pre-event: Confirming of consent and baseline data (for those who did not use online option consenting and baseline data will be done). Vitals (i.e. height, weight, heartrate, temperature, blood pressure), physiological data (i.e. HRV, EEG, wearables), and biological data (i.e. saliva, blood) will be collected from all consented subjects and controls.

During event: Data collection during the event may include additional collection of questionnaire data, physiological data and biological data.

Immediate post-event: Vitals (i.e. height, weight, heartrate, temperature, blood pressure), physiological data (i.e. HRV, EEG, wearables), and biological data (i.e. saliva, blood) will be collected from all consented subjects and controls.

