# 8 Data Analysis

Demographic characteristics will be analyzed by descriptive statistics. Survey data are collected on an ordinal 4-point or 5-point Likert scale and treated as continuous variables during analysis. The data is then analyzed to describe the distribution. If the data is normally distributed, we will follow up with utilizing parametric statistics. However, if the data does not follow a classic normal distribution, we will utilize other methods such as reporting the median instead of the mean for central tendency and further analyze our results with frequencies, contingency tables, chi-square-tests, Spearman rho assessment, or the Mann-Whitney U test. All other questionnaires will be analyzed according to published protocols.

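### Experiment B draws on repeated events, but controls are matched on age and sex only and the named group tests take no account of event; if events are pooled at unequal subject-to-control ratios, part of any between-event difference enters the subject-control contrast.

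*Protocol*

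**What the plan says.** Section 6.1.2 says "We therefore aim to collect data before, during, and after a meditation event that take place nationally and internationally on a regular basis", so more than one event can contribute. The number of events is not given. The same section says that the event setting keeps confounding factors such as diet, housing and sleep to a minimum. Section 1 makes a similar claim, adding climate, circadian pattern and daily routine.

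On numbers, Section 6.3.2 says "Depending on the event, we anticipate recruiting between 10 to 100 subjects" and "We anticipate recruiting between 5 and 20 control subjects". The first range is tied to the event. The second is not, and could be per event or overall.

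Controls are found by asking participants whether they are "traveling with family/friends who will be at the event but will not participate in the event". The matching rule is "Controls will be age and sex matched to match subjects"; event is not a matching factor. Vitals, physiological and biological data immediately before and after the event "will be collected from all consented subjects and controls".

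Section 8 calls for parametric statistics, with no model named, when data are normal. Otherwise it gives methods such as "chi-square-tests, Spearman rho assessment, or the Mann-Whitney U test". Section 10 refers back to Section 8. Neither section mentions event.

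**The concern.** Housing, diet, climate and routine are alike for subjects and controls within one event, not across events in different countries and at different times. The benefit claimed in Sections 1 and 6.1.2 therefore depends on comparing each subject with controls from the same event. The matching rule does not require this, and chi-square and Mann-Whitney U in their usual form compare two undivided groups.

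Two features of the protocol make event differences plausible. Section 6.4 provides for two EEG manufacturers, with no rule on how devices are spread over events or groups. Section 6.7.2 has blood iced, rested, centrifuged and aliquoted after collection, so handling may vary with location. If one event supplies most of the subjects and another most of the controls, such differences would appear as an effect of meditation.

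**Working it through.** The protocol states no sample size, power or error-rate calculation, so there is no figure of its own to reproduce.

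**Inputs.** Subjects per event: 10 to 100 (Section 6.3.2). Controls: 5 to 20 (Section 6.3.2), read here as per event. Between-event difference D: not in the protocol, so assumed at 0.2 to 0.5 SD for the bias and at 0.5 and 1 SD for the error rates.

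**Range of ratios.** On the per-event reading the ranges permit anything from 10/20 = 0.5 to 100/5 = 20 subjects per control. If controls rise with subjects, the range is 10/5 = 2 to 100/20 = 5.

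**Bias.** Take two pooled events and no effect of meditation. Then

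bias = (share of subjects at event 1 − share of controls at event 1) × D.

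- 40:20 with 10:5: 40/50 − 20/25 = 0.80 − 0.80 = 0
- 100:20 with 10:5: 100/110 − 20/25 = 0.909 − 0.80 = 0.11
- 100:10 with 50:10: 100/150 − 10/20 = 0.667 − 0.50 = 0.17
- 100:10 with 10:10: 100/110 − 10/20 = 0.909 − 0.50 = 0.41
- 60:5 with 30:15: 60/90 − 5/20 = 0.667 − 0.25 = 0.42
- 100:5 with 10:20: 100/110 − 5/25 = 0.909 − 0.20 = 0.71

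With D from 0.2 to 0.5 SD, the last case gives 0.709 × 0.2 = 0.14 to 0.709 × 0.5 = 0.35 SD. The 60:5 with 30:15 case gives 0.417 × 0.2 = 0.08 to 0.417 × 0.5 = 0.21 SD. The 100:20 with 10:5 case gives 0.109 × 0.2 = 0.02 to 0.109 × 0.5 = 0.05 SD. For change scores the same formula holds, with D as the event difference in mean change.

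**Error rate.** Simulated two-sided type I error at a nominal 0.05 (4000 runs, normal outcome, SD 1), pooled Mann-Whitney U against a rank test stratified by event (van Elteren):

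| Events | Pooled, D = 0.5 | Pooled, D = 1 | Stratified, D = 0.5 / 1 |
|---|---|---|---|
| 40:20 with 10:5 | 0.04 | 0.04 | 0.048 / 0.050 |
| 100:20 with 10:5 | 0.05 | 0.07 | 0.049 / 0.052 |
| 100:10 with 50:10 | 0.06 | 0.07 | 0.049 / 0.052 |
| 100:10 with 10:10 | 0.13 | 0.31 | 0.052 / 0.048 |
| 100:5 with 10:20 | 0.32 | 0.84 | 0.052 / 0.056 |

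The stratified test stays near 0.05 throughout. The pooled test stays near 0.05 only when the ratios are equal or not far apart.

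**The case against.** There is a good case on the other side, and much of it stands.

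- **Controls belong to the event.** They are people present at it, measured immediately before and after it alongside the subjects. A reader might infer that site, season and event length are confounded with being a meditator by design. The documents do not support that: within an event both groups share these, and the protocol describes neither seasons nor event lengths.
- **Pooling is not stated.** Separate analysis of each event fits the text equally well, and then the problem does not arise.
- **Unequal ratios are inferred.** The protocol gives two anticipated ranges and no ratio by event. The 0.71 figure needs opposite ends of both ranges, including an event with two controls per subject. With less extreme ratios the effect is small.
- **Section 8 does not rule out stratification.** A reader might infer that the planned methods cannot stratify. That is true only of the named tests in their usual form. The parametric branch names no model, and the other list is illustrative.
- **Pre-post change removes stable event differences.** This is correct. What remains is any event difference in change, for example from event length. Section 8 does not commit to change scores for the subject-control comparison.
- **An analysis plan may add an event term.** It may, and its absence from the protocol alone would be no finding. The matching rule and the meaning of the control number, however, are design matters set in Section 6.3.2. An analysis plan cannot supply within-event controls that were not recruited.

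**Conclusion.** The point holds as a conditional one. It requires three things together: events are combined, subject-to-control ratios differ between them, and the outcome (or its change, where change is analysed) differs between events. Given these, the fraction of the event gap that enters the contrast runs from 0 at equal ratios, through 0.11 at 100:20 with 10:5, to 0.71 at 100:5 with 10:20. These fractions rest on two events and on reading 5 to 20 as per event. If it is a total, an event may have few or no controls and the fraction can be larger. The conversions to SD units and error rates rest also on the assumed event gaps.

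The protocol allows this loss of within-event control without requiring it. A reader might also infer that controls must be enrolled at every event. That does not follow: an event without controls does no harm to the contrast if it is left out of it. For an exploratory pilot this does not undermine the study, but it is worth correcting because the protocol relies on the event setting for its claim of good control and the remedy costs little.

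**What to change.** **Section 6.3.2, control selection:** match controls to subjects within the same event, as well as on age and sex, and state whether 5 to 20 is per event or in total.

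**Section 8:** add that, when events are combined, the subject-control comparison is made within event. In the parametric model, enter event as a fixed effect. For non-normal outcomes, use a van Elteren rank test stratified by event in place of Mann-Whitney U. Events without controls then contribute nothing to this contrast, though their data remain usable for other descriptions.

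**Cost:** event is already known for every participant, so the analysis change is a sentence or two. Within-event matching follows from how controls are already sought. The downside is that events without controls drop out of the controlled comparison, with a small loss of precision.

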6.1.3 Experiment C (Measuring the effects of meditation within the meditation community)

Under this exploratory paradigm, we are interested in collecting data within members of [name] meditation community. Given the large size and diversity of this global community, practicing the same meditative practice, we will be able to generate a set of interesting pilot data.

## 6.2 Timeline

6.2.1 Experiment A (Measuring the effects of meditation on the Healer and Healee)

For qualifying subjects, consenting as well as data collection will be performed electronically prior to the event. For both Healers as well as Healees, we will collect a set of baseline measures, including demographics, medical history, and questionnaire data.

The baseline will be collected in a timeframe after consenting but before the first healing event. After the healing event, we will collect outcome date at different timepoints (i.e. immediately after healing event, 1, 3, 6, 9, 12 months out). These data will be collected electronically. If baseline data collection also included physiological and/or biological data, we may collect these follow-up data at the above time points as well.

6.2.2 Experiment B (Measuring the effects of meditation on the human organism)

The timeline, as outlined in Figure 1, is divided into pre-event, immediate pre-event, during event, immediate post-event, and post-event.

Pre-event: For qualifying subjects and controls, consenting as well as baseline data collection will be performed electronically prior to the event.

Immediately pre-event: The data collection is organized into 4 stations.

Station 1:

- Confirming of consenting and baseline data (for those who did not use online option, consenting and baseline data will be done.)
- Vitals

Station 2:

• Physiological data (i.e. HRV, wearables)

Station 3:

• Physiological data (i.e. EEG)

Station 4:

• Biological data (i.e. saliva, blood)

During the event: Data collection during the event may include additional collection of questionnaire data, physiological data, and biological data.

Immediately post-event: The data collection is organized into 4 stations.

Station 1:

- Vitals
- Questionnaire data

Station 2:

• Physiological data (i.e. HRV, wearables)

Station 3:

• Physiological data (i.e. EEG)

Station 4:

• Biological data (i.e. saliva, blood)

Post-event: follow-up data may be collected electronically. Time points may include 1,3, 6, 9, 12 months post-event. If baseline data collection also included physiological and/or biological data, we may collect these follow-up data at the above time points as well.

Pre-event	Screening Questionnaires	Online
	Consent	
	Baseline Questionnaire data	
Immediate Pre-event	• Consent and baseline questionnaire	In-Person
	data (for those who did not utilize	
	online)	
	Vitals	
	
 
Physiological readouts (i.e. HRV, EEG,
 
	
	wearable data)	
	
 
Biological data (i.e. saliva, blood)
 
	
During event	Questionnaire data	In-Person
	• Physiological readouts ( i.e. HRV, EEG,	
	wearable data)	
	
 
Biological data (i.e. saliva, blood)
 
	
Immediately Post-event	Questionnaire data	In-Person
	Vitals	
	• Physiological readouts ( i.e. HRV, EEG,	
	wearable data)	
	
 
Biological data (i.e. saliva, blood)
 
	
Post-event	
 
Follow-up questionnaire data
 
	Online
	
 
Physiological readouts (i.e.
 
	
	wearables)	
	Biological data ( i.e. saliva)	

Figure 1: Timeline

#### 6.2.3 Experiment C (Measuring the effects of meditation within the meditation community)

In this exploratory paradigm, we will include studies collecting data among [name] meditation community. We will focus on gathering pilot data (i.e. questionnaires and wearable data) of long term effects of meditation on human well-being and function. The duration may span from several weeks to several months.

## 6.3 Experimental Protocol

6.3.1 Experiment A (Measuring the effects of meditation on the Healer and Healee)

Subject selection:

Healer: Members of [name] meditation community who meet inclusion/exclusion criteria qualify to participate. Depending on the healing event, we anticipate recruiting between 10 to 100 Healers.

For Healers, consenting as well as baseline data collection will be performed electronically prior to the event. The consent form will be provided to the selected Healers for review. The PI or designated research staff member will go over the consent form in person or via HIPAA

compliant web meeting platform (ie. Zoom). During this time, Healers will have ample time to have all questions and concerns addressed. We may also collect baseline measures including physiological readouts (i.e. wearables, HRVs) and/or biological data (i.e. saliva). During the healing event, we may collect physiological readouts (i.e. EEG, HRV), biological data (i.e. saliva) and questionnaire data. After the healing event, follow-up data will be collected electronically. Time points may include immediately after, 1,3, 6, 9 12 months post event. If baseline data collection also included physiological and/or biological data, we will collect these follow-up data at the above time points as well.

Healee: A list of Volunteers who are interested in participating in a healing event will be provided by [name] staff. From that list, participants who meet the inclusion/exclusion criteria will be recruited: we anticipate recruiting up to 100 to 150 participants.

For Healees, consenting as well as baseline data collection will be performed electronically prior to the event. The consent form will be provided to the selected Healees for review. The PI or designated research staff member will go over the consent form via HIPAA compliant web meeting platform (ie. Zoom). During this time, Healees will have ample time to have all questions and concerns addressed. We may also collect baseline measures including physiological readouts (i.e. wearables, HRVs) and/or biological data (i.e. saliva). Immediately prior to the healing event, [name] guides the Healees through a meditation to prepare them for the healing event. During the healing event, Healees will listen to music. After the healing event, follow-up data will be collected electronically. Time points might include immediate after, 1,3, 6, 9 12 months post event. If baseline data collection also included physiological and/or biological data, we will collect these follow-up data at the above time points as well.

